## INTRODUCTION

Stereotypes and stereotype threat are two important issues that have been studied repeatedly in the psychology literature. Stereotype threat is the thought that a person will be negatively evaluated and judged regarding a negative stereotype that belongs to the group to which he/she belongs (1). Most people are members of a social group associated with at least one negative stereotype. Therefore, many people in society may be the target of stereotype threat. Previous research has shown that the individual performance of people in groups identified with negative stereotypes, who are exposed to stereotype threat, decrease. The stereotype threat may arise when there is an environment in which the skills of the person that may be affected by a stereotype associated with his/her group can be measured, or if this stereotype has become evident (2, 3).

Researchers have shown that different methods can be effective in the emergence of stereotype threat. Steele and Aronson (1) show that even a question about the group membership (e.g. race) can reveal the stereotype threat. Considering the stereotype threat studies, a triple classification can be made for the manipulations used as (a) explicit, (b) partially explicit, and (c) indirect/implicit (4). When it is emphasized that one group is inferior or unsuccessful compared to the other group (e.g. men outperform women on this math test) it is possible to say that this is overt stereotyping manipulation. If the participants are told that there are group differences in the task without specifying the direction of the group difference (e.g. men and women perform differently on this math test), it is possible to classify this as partially explicit stereotyping manipulation. Indirect/implicit stereotyping manipulations emphasize the diagnostic nature of the test (e.g. it is an intelligence test) or ask the participant's group identity before performing.

The mechanism of the stereotype threat is still unclear. Previous studies have shown that many factors (anxiety, negative cognitions, low-performance expectations, physiological arousal, reduced memory capacity, etc.) work together to influence stereotypical threat in some contexts (5). Schmader et al. published an integrated model to explain the mechanism of stereotype threat

(6). This model focused on three interrelated factors: stress stimulation, performance monitoring, and efforts to suppress thought-emotions.

Due to the SARS-CoV-2 (Covid-19) pandemic, there has been a rapid increase in the number of intensive care patients in our country and around the world since March 2020 (7). Due to this rapid increase, the number of intensivists physicians is insufficient, and non-intensivist physicians from various branches are assigned to ICU. In social media and newspaper reports, it was stated that non-intensivist physicians have insufficient knowledge and skills in intubation and in the treatment of lung infection, and the public was asked to take precautions (8,9). However, these physicians were expected to treat lung infections and intubate the patients in ICU during pandemic. It is unknown to what extent such negative stereotypes, established or already existing, affect the performance of non-intensivist physicians during their appointment to the ICU during the pandemic.

As in all other departments, the most basic task expected from doctors in ICU is effective basic life support applied for the treatment of cardiopulmonary arrest. Cardiopulmonary resuscitation (CPR) is a basic life support model that is mandatory taught in medical schools. For this reason, it is expected that all doctors, regardless of their specialties, will be able to perform CPR effectively. The use of manikins is quite common in order to standardize CPR training and performance measurement (10,11).

The aim of this study is to evaluate how non-intensivist physicians assigned to intensive care units during the pandemic are affected by stereotype threat and to investigate the necessary conditions to prevent a possible decrease in performance in these physicians.

## **MATERIAL AND METHODS**

### **Participants**

The participants of our study will consist of Hacettepe University Faculty of Medicine resident doctors assigned to the Covid-19 ICU during the pandemic. Participants will consist of two groups as who did not work in the ICU during their medical training (non-intensivists) and who work in the ICU during their medical training (intensivists). Participants will be invited to study with an announcement text (Appendix 1: Announcement Text). Those who agree to participate will be included in the study.

### **Method**

The study will consist of two parts. The first part will have a qualitative design (interview). The second part will be a randomized controlled study design (mannequin study). Participants' ages, genders, branches, working years and previous CPR experiences will be recorded (Appendix 2: Data Collection Form).

### ***Part One: Interview***

In the first part, an independent psychologist will conduct a semi structured online interview with 15 randomly selected participants from non-intensivist group about working conditions in ICU and negative stereotypes about performants of non-intensivist physicians in ICU during the pandemic period (Appendix 3: Interview Questions). Participants participating in the interview will not be included in the mannequin study.

### ***Part Two: Mannequin Study***

In the second part, both the intensivist and the non-intensivist groups will be randomly divided into two subgroups as experiment and control. Then, stereotype threat manipulation will be performed on experimental group just before they are taken into the testing room. For manipulation, the following sentences will be said: “Studies have shown that intensive care workers are more successful in CPR. In this study, we aim to compare the CPR performance between ICU and other branches.”. The other group (Control Group) will not be given any prior information.

All participants will play a standard CPR simulation scenario under the supervision of an intensivist physician who is blind to the groups. Participants' performance will be measured with a CPR simulator mannequin (Resusci Anne Simulator®, 'Laerdal Medical'). All performants will be videotaped during simulation. Later, these videotapes will be evaluated and scored separately by three independent resuscitation instructor anesthesiologists who are blinded to groups (Appendix 4: CPR Evaluation Form). The total simulation score will be obtained by adding the objective scores obtained from the simulator's data (Appendix 5: Mannequin Scores) to the average subjective scores of the independent resuscitation instructors.

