### **Analysis of data**

Simulation CPR scores will be the dependent variable. Being an intensivist or non-intensivist and stereotype threat will be the independent variables of the study. There will be four groups to be compared: intensivist in the experimental group (1), intensivist in the control group (2), non-intensivist in the experimental group (3), non-intensivist in the control group (4). Age,

gender, years of employment, previous resuscitation experience and CPR certificates will be the control variables. Baseline data between groups will be analyzed by the 2x2 between subject factorial ANCOVA. The data will be checked taking into account two-way factorial ANCOVA assumptions. The correlation between the simulation scores and the control variables such as age, number of previous CPR experiences, etc. will be analyzed by Spearman Analysis. If the control variables significantly associate with the dependent variables, they will be included to the main analyses, factorial ANCOVA. P values less than 0.05 will be considered significant.

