## **APPENDIX 1: ANNOUNCEMENT TEXT**

We are looking for volunteer residents who were previously assigned to ICU during Covid-19 pandemic, for a mannequin study titled "Assessment of Cardiopulmonary Resuscitation Skills with Simulation in ICU". Those who want to participate in the study can apply to [name] [name].

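### Only the experimental arm is addressed before testing, so the simple and main effects estimate the whole message versus no scripted message; a neutral control statement is a cheap improvement

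*Combined protocol and SAP*

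**What the plan says.** Part Two: Mannequin Study randomises intensivists and non-intensivists separately to experiment or control. For the first of these, "stereotype threat manipulation will be performed on experimental group just before they are taken into the testing room". The message has two sentences. One states that intensive care staff do better at CPR; the other is "In this study, we aim to compare the CPR performance between ICU and other branches". For controls, "The other group (Control Group) will not be given any prior information". Neither the method nor the five appendices contain a neutral script.

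Analysis of data labels the factors as follows: "Being an intensivist or non-intensivist and stereotype threat will be the independent variables of the study". It adds "There will be four groups to be compared", a 2x2 factorial ANCOVA and a 0.05 significance level. It does not say whether the simple effect in non-intensivists, the message main effect or the interaction answers the aim. The Introduction gives that aim as to "evaluate how non-intensivist physicians assigned to intensive care units during the pandemic are affected by stereotype threat".

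**The concern.** The arms differ in stereotype content, but also in whether anyone speaks to the participant about the study immediately before the test. The Introduction lists anxiety, physiological arousal and performance monitoring among possible mechanisms. It is plausible, though the documents do not show it, that being addressed at that moment acts on these without any stereotype. If so, a difference that the analysis labels stereotype threat could be partly or wholly something else, or a real threat effect could be partly hidden. Because no contrast is tied to the aim, the reading would also depend on which of three estimates is put forward.

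**Working it through.** The plan states no sample size, SD, effect size or power for the mannequin study, so there is no figure to reproduce. All effect values below are assumptions, in score points.

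**Scale.** Appendix 4 has 9 items and Appendix 5 has 3, each scored 1 to 4. If items are summed (and Appendix 4 is averaged over raters), the total runs from 12 × 1 = 12 to 12 × 4 = 48. One point is 1/36 = 2.8% of the range.

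**Message length.** The two scripted sentences have 12 + 15 = 27 words; controls have 0.

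**Contrasts.** Let t be the threat effect of the message in non-intensivists, l any lift it gives intensivists, and gN and gI the non-specific effects of being addressed in non-intensivists and intensivists. Then:

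- simple effect in non-intensivists = t + gN
- message main effect (equal weights) = (t + l + gN + gI)/2
- interaction = (t + gN) − (l + gI) = t − l + gN − gI

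| t | l | gN | gI | Simple | Main | Interaction |
|---|---|---|---|---|---|---|
| 0 | 0 | -1 | -1 | -1 | -1 | 0 |
| 0 | 0 | +1 | +1 | +1 | +1 | 0 |
| -2 | 0 | 0 | 0 | -2 | -1 | -2 |
| -2 | 0 | -1 | -1 | -3 | -2 | -2 |
| -2 | 0 | +1 | +1 | -1 | 0 | -2 |
| -2 | 0 | -1 | 0 | -3 | -1.5 | -3 |
| -2 | +2 | 0 | 0 | -2 | 0 | -4 |
| 0 | +1 | -1 | -1 | -1 | -0.5 | -1 |

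Row 1 shows apparent threat where there is none; row 5 shows threat half hidden. In both, the interaction recovers t. Row 6 shows that it does not when gN and gI differ. Row 7 gives three different answers from one truth with no non-specific effect at all. Row 8 shows that intensivist lift can make the interaction negative when t is 0.

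**Precision.** With n per cell and a common SD, the standard errors are SD√(2/n) for the simple effect, SD√(1/n) for the main effect and SD√(4/n) for the interaction. The interaction's standard error is √2 = 1.41 times that of the simple effect.

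**Should the interaction be tested only after a significant simple effect?** Assume 30 per cell, SD 4 and two-sided 0.05.

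- Row 5: the simple effect is -1 with standard error 4√(2/30) = 1.03, and the interaction is -2 with standard error 4√(4/30) = 1.46. Power for the interaction is 0.28 on its own and 0.12 if gated.
- Row 1: the simple effect is significant 16% of the time with no threat effect (10% to 39% over 20 to 50 per cell and SD 3 to 5).

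Gating would therefore make the protected contrast wait on the unprotected one. Treating the two as interchangeable claims, each at 0.05, gives a 0.083 chance of at least one false positive (equal cells, normal approximation). One of them should therefore be named as answering the aim.

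**The case against.** The strongest reply is that this is a legitimate design choice. The Introduction classes statements of group inferiority, and statements that groups differ, as threat manipulations. Both sentences of the message therefore belong to the manipulation, and only the act of being spoken to is left as non-specific. Nothing in the documents shows that this alters CPR performance. Intensivists hear the same message and serve as a comparison, and the 2x2 model ordinarily yields the interaction. Nor are controls wholly uninformed: Appendix 1 invites every volunteer to a study titled "Assessment of Cardiopulmonary Resuscitation Skills with Simulation in ICU". Consent pages are absent from the text reviewed, so what else both arms were told cannot be judged.

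Most of this stands. It is why the contrast should be called no scripted message rather than no information, and why the branch comparison should stay out of any control script. It does not remove the point, because the protection lies in the interaction alone, depends on gN = gI, and is not designated in the plan.

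A reader might infer that the randomised comparison is confounded, or that the trial cannot address stereotype threat. The documents do not support that. Allocation is random within each group, the supervisor and video raters are blinded, and message versus no scripted message is a valid causal contrast. Only its attribution is open.

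**Conclusion.** The point holds as one of interpretation, with medium confidence. As planned, the non-intensivist simple effect and the message main effect are whole-message effects and cannot be credited to stereotype content alone. The algebra is exact. The size is unknown: a non-specific effect of g points common to both groups shifts the simple and main effects by g and leaves the interaction unchanged. Any figure for g is an assumption.

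The unnamed contrast is mainly a gap in detail and would carry little weight alone. It matters here because the three candidate estimates respond differently to a non-specific effect. The sponsor should make the change because it is cheap and sharpens the answer to the trial's own question, not because the design is invalid.

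**What to change.** **Part Two: Mannequin Study.** Leave the experimental message as it is. Replace the control sentence with:

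> At the same point, the same person says to the control group a neutral statement of equal length that makes no mention of performance, evaluation or branch differences, for example: *Manikins are commonly used to standardize CPR training. In a moment, we will take you from here and go into the testing room.*

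The example has 8 + 15 = 23 words, so it needs four filler words to reach 27. Beginning it *Manikins of various kinds are commonly used to help standardize CPR training* gives 12 + 15 = 27. The content follows the Introduction, which says "The use of manikins is quite common in order to standardize CPR training and performance measurement". A sentence about assessing performance should not be added to either arm: it would alter the experimental message, and the Introduction counts emphasis on the diagnostic nature of a test as implicit threat.

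**Analysis of data.** Add:

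> The experiment-control difference in non-intensivists, from the 2x2 ANCOVA, is the contrast that answers the aim. The group-by-message interaction is reported with its confidence interval as a supporting check, whether or not the first contrast is significant; it estimates the threat effect minus any intensivist lift. The message main effect is secondary.

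**If the control condition cannot be changed,** describe simple and main effects as whole message versus no scripted message, and attribute an effect to stereotype threat only where the interaction supports it. Row 8 of the table shows that even this is not proof, so the intensivist difference should be shown alongside.

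**Cost.** Two spoken sentences and a few lines of text, with no added participants, staff or procedures. The contrast becomes threat message versus neutral message rather than versus silence. The match in non-specific effect is only approximate, intensivist lift remains in the interaction, and the interaction is the less precise check (1.41 times the standard error with equal cells and variances).

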### **Analysis of data**

Simulation CPR scores will be the dependent variable. Being an intensivist or non-intensivist and stereotype threat will be the independent variables of the study. There will be four groups to be compared: intensivist in the experimental group (1), intensivist in the control group (2), non-intensivist in the experimental group (3), non-intensivist in the control group (4). Age,

gender, years of employment, previous resuscitation experience and CPR certificates will be the control variables. Baseline data between groups will be analyzed by the 2x2 between subject factorial ANCOVA. The data will be checked taking into account two-way factorial ANCOVA assumptions. The correlation between the simulation scores and the control variables such as age, number of previous CPR experiences, etc. will be analyzed by Spearman Analysis. If the control variables significantly associate with the dependent variables, they will be included to the main analyses, factorial ANCOVA. P values less than 0.05 will be considered significant.

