## **APPENDIX 2: DATA COLLECTION FORM**

1. Participant Number:
1. Group: Experiment/Control
2. Age:
3. Gender:
4. Medical Branch:
5. Years of residency:
6. Number of CPR experiences:
7. Number of CPRs performed during Covid-19 ICU
8. Working time in Covid-19 ICU
9. Do you have a basic life support training certificate after graduation? Yes/No

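### An outcome-based Spearman screen chooses the ANCOVA covariates, so what the non-randomised intensivist comparison is adjusted for is left to chance

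*Combined protocol and SAP*

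**What the plan says.** In the combined protocol and SAP, Analysis of data, the simulation CPR score is the dependent variable and both factors are of interest: "Being an intensivist or non-intensivist and stereotype threat will be the independent variables of the study". Age is listed as a control variable, and the sentence continues: "gender, years of employment, previous resuscitation experience and CPR certificates will be the control variables".

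None of the five is fixed in the model. The score's correlation with "control variables such as age, number of previous CPR experiences, etc. will be analyzed by Spearman Analysis", and then: "If the control variables significantly associate with the dependent variables, they will be included to the main analyses, factorial ANCOVA". The only threshold in the section is P<0.05. The correlation is not said to be computed within specialty, and the word etc. leaves the screened list open.

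The two factors arise differently. Under Participants, the groups are those "who did not work in the ICU during their medical training (non-intensivists) and who work in the ICU during their medical training (intensivists"), so specialty is a pre-existing characteristic. Under Part Two: Mannequin Study, "both the intensivist and the non-intensivist groups will be randomly divided into two subgroups as experiment and control", so threat is randomised within specialty.

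**The concern.** Randomisation protects the threat comparison whether or not covariates are in the model. It does not protect the intensivist comparison, where covariate adjustment is the only safeguard the plan offers.

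The screen is poorly matched to that job, for three reasons:

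- It asks whether a variable correlates with the score, and ignores whether the variable differs between specialties.
- In a small sample, a non-significant correlation does not show that a variable is harmless.
- A correlation pooled over specialties mixes the within-specialty slope with the between-specialty gap. If these act in opposite directions, a real association can be hidden.

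At stake are bias in the adjusted intensivist effect and a model whose meaning varies with the data: the same plan could give an effect adjusted for experience in one sample and unadjusted for it in the next.

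**Working it through.** **Inputs.** The plan gives the two factors, five candidate covariates, the Spearman rule and the 0.05 threshold. It gives no sample size for the mannequin study, no SD, no effect size and no correlations, so there is no stated figure to reproduce. Everything below is assumed: equal cells, usually 20 per cell (N = 80), within-specialty outcome SD 1, two-sided tests. The screen pools all participants and is compared with a model that always contains all five covariates.

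**1. How masking works.** Take one covariate with within-specialty SD 1, slope b = 0.3, specialty shift d = 0.8 SD, and specialty effect g at equal covariate values. Pooled over two equal specialty groups:

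- covariance of covariate and score = b(1 + d²/4) + g·d/4
- variance of covariate = 1 + d²/4 = 1.16
- variance of score = 1 + (g + b·d)²/4

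With g = 0, the covariance is 0.3 × 1.16 = 0.348 and r = 0.348/√(1.16 × 1.0144) = 0.32.

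With g = -0.6, the covariance is 0.348 - 0.12 = 0.228 and r = 0.228/√(1.16 × 1.0324) = 0.21.

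The covariate matters equally in both cases, but the screen sees a weaker signal in the second. Using Fisher's z, the chance of passing is about Φ(√77 × atanh r - 1.96), which is 83% and 46%. Simulating the Spearman test itself (4,000 replicates) gave 80% and 40%.

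**2. What dropping it does.** Each omission shifts the intensivist effect by about b·d = 0.3 × 0.8 = 0.24 SD. With 60% of trials omitting it, the crude average is 0.60 × 0.24 = 0.14 SD. The simulated mean bias is 0.12 SD, slightly lower because omission is likelier when the sample association is weak. Power for the intensivist effect is 56% with the screen and 71% with all five fixed, where bias is about zero. Without masking (g = 0), mean bias is only 0.02 SD and type I error is 5.4% against 5.0%.

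**3. Type I error for the intensivist factor** (no gap at equal covariate values, 20 per cell, 10,000 replicates, simulation SE about 0.2 points):

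| Assumed structure | Screen | All five fixed | Excess |
|---|---|---|---|
| Two covariates, slope 0.2, opposite 0.5 SD shifts | 5.3% | 5.0% | 0.3 |
| Experience and certificate, slope 0.2 each, 0.5 SD shifts | 6.5% | 5.5% | 1.0 |
| Experience, slope 0.2, 1 SD shift (passes the screen 47% of the time) | 5.8% | 4.7% | 1.1 |
| Experience 0.3 and age -0.3, both shifted 1 SD | 6.3% | 5.2% | 1.1 |
| Two independent covariates, slope 0.3, opposite 1 SD shifts | 9.1% | 4.8% | 4.3 |
| Five independent covariates, slope 0.2, each shifted 0.5 SD the same way | 9.6% | 5.0% | 4.6 |

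A separate 4,000-replicate run of the last two rows gave 9.2% against 4.9% and 8.6% against 4.4%. In the fifth row the mean bias is about zero. The excess arises because the screen sometimes keeps only one of two offsetting covariates, which moves the estimate by about 0.3 SD in either direction.

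**4. Threat and interaction.** In the 10,000-replicate runs, type I error under the screen was 4.7-5.4% for threat and 4.6-5.4% for the interaction. Power for threat/interaction (20 per cell, threat effect 0.8 SD in non-intensivists only, 6,000 replicates, SE about 0.6 points):

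| Assumed structure | Screen | All five fixed |
|---|---|---|
| Overlapping; experience 0.3, certificate 0.2, years 0.1 | 46/46% | 47/47% |
| Overlapping; all five at 0.15 | 45/46% | 46/47% |
| Overlapping; experience only, 0.4 | 48/46% | 47/45% |
| Independent; three at 0.25 | 45/47% | 48/49% |
| Independent; all five at 0.25 | 48.5/46.5% | 54.5/53.5% |
| None prognostic | 42/42% | 40/40% |

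Overlapping means assumed correlations of 0.7 (age and years), 0.6 (years and experience) and 0.4 (age and experience), with gender and certificate binary.

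**The case against.** **The aim lies elsewhere.** The Introduction asks how stereotype threat affects non-intensivists. That question rests on the randomised threat effect and its interaction with specialty, which the screen leaves valid. This stands, and it limits the weight of the point. But the plan also makes intensivist status an independent variable of the main analysis, so its estimate will be reported and read.

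**The covariates may not be confounders.** Intensivists are defined by ICU work during training, and the data collection form asks for "Number of CPR experiences" and for a life support certificate obtained after graduation. Both may partly be consequences of that training. With a specialty gap running wholly through experience (slope 0.4, 1 SD shift, 20 per cell), an unadjusted 2x2 analysis detects it 42% of the time, all five fixed 4.7% and the screen 4.9%. This also stands. It does not rescue the screen, which hides such a gap just as much. It does mean that the fix must state what the adjusted effect means.

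**The excess is small in ordinary structures.** Four of the six type I scenarios show about 1 point or less; the larger figures need independent covariates with large opposing shifts, or all five shifted. Fair, and the range should be quoted whole.

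**Stronger readings to avoid.** A reader might infer that selecting covariates on the outcome inflates the false-positive rate of the threat test or the interaction. Threat is randomised within specialty, and the simulations show no inflation. A reader might also infer a general loss of power for threat. That loss is about one point or none when covariates overlap, as age, years of residency and CPR count probably do among residents, and it reverses when none is prognostic.

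**Conclusion.** The concern holds for the intensivist factor. The screen can remove a variable that differs between specialties and affects the score, so the adjusted comparison can be biased and its adjustment set depends on chance. Under the assumptions above, the type I excess runs from under 1 to about 4-5 percentage points. The masked example gives 0.12 SD of bias and a fall in power from 71% to 56%. These figures show the mechanism and a range. They do not estimate what will happen in this trial, because the documents supply no sample size, SD or correlations.

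The randomised threat and interaction tests remain valid. Their power falls materially only if several covariates are mutually independent and prognostic: by 4-7 points with five such covariates of 0.25 at 15-30 per cell. The change is worth making because it is cheap and removes an arbitrary step; the main randomised result is not in doubt.

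**What to change.** In Analysis of data:

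1. Delete the Spearman correlation as an inclusion rule and keep the correlations as descriptive results.
2. Enter all five control variables in the main ANCOVA whatever their p-values, each tied to one item of Appendix 2: age; gender; years of employment, taken as "Years of residency"; previous resuscitation experience, taken as "Number of CPR experiences"; and the yes/no question on a basic life support certificate.
3. State that experience and certificate may partly result from ICU training, so the adjusted intensivist effect is the gap at equal values of these variables. Also report the intensivist comparison without those two.

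A shorter fixed list is not a safe substitute. Fixing only years, experience and certificate gave intensivist type I error of 13.2% against 9.6% for the screen with five confounders, and 22.1% against 6.3% when age was an omitted confounder.

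The cost is a few sentences and no new data. The statistical price is up to five degrees of freedom: about 1-2 points of power if no covariate is prognostic. In very small samples there may be no gain in power either. At 10 per cell with overlapping covariates, threat/interaction power was 24/24% under both rules with three prognostic covariates (experience 0.3, certificate 0.2, years 0.1), and 22/22% for the screen against 20/20% with none prognostic.
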